**Table 8: Illustration of D1 and D2 Criteria**

If the last tumor assessment before the event date occurs between Study Days	D1	D2
1 – 21	49	91
22 – 63	56	112
$\geq 64$	70	126

*Example: For a patient with a tumor assessment SD at Day 21 (last tumor assessment before PFS event), and PD at the next tumor assessment on*

- *Scenario 1: Day 46 (i.e. 25 days after SD). Patient is classified as not having missed tumor assessment between both scans. PFS is not censored.*
- *Scenario 2: Day 76 (i.e. 55 days after SD). Patient is classified as having missed 1 tumor assessment between both scans. PFS event is not observed after more than 1 missing or inadequate tumor assessment. PFS is not censored.*
- *Scenario 3: Day 113 (i.e. 92 days after SD). Patient is classified as having 2 missing tumor assessments between both scans. PFS event is observed after more than 1 missing or inadequate tumor assessment. Using the D2 definition, PFS is censored at the last adequate tumor assessment (at SD scan).*

#### 9.4. BASELINE

*Baseline* is defined as the last available assessment before the first study treatment administration, unless otherwise specified.

If an assessment is planned to be performed prior to the first dose of study treatment in the protocol and the assessment is performed on the same day as the first administration of study drug, it will be assumed that it was performed prior to study treatment administration (if time is not available).

Unscheduled assessments will be used in the determination of baseline.

ECG Baseline will be the mean of the triplicate measurements at Cycle 1 Day 1 before the first study treatment administration.

Change from baseline will be defined as the difference between the value of the endpoint at the time point of interest and the baseline value.

## 9.5. CUT-OFF CONVENTIONS

All available data will be included at the time of the cut-off date.

Subjects continuing to receive study treatment at the time of analysis will have time-to-event data (e.g., PFS, DOR) censored at the time of last tumor assessment prior to the data cut-off point used, if the event has not been observed before. Ongoing events (e.g., AEs, concomitant medication, etc.) will be summarized for analysis using the data cut-off date as the date of completion, with an indication that the event is ongoing.

For subjects who drop out from the study with ongoing events, the discontinuation date will be used as the completion date of the event with the appropriate censoring.

Data obtained after the cut-off will not be displayed in any listings or used for summary statistics (e.g. laboratory values of samples taken after data cut-off, AE with onset date after data cut-off, etc.).

For exposure data, if the treatment was started before the cut-off date and ended after the cut-off date, the end date will be imputed by the cut-off date. This imputed date will be used for duration and cumulative dose derivations.

## 10. DEVIATIONS AND ADDITIONAL REASONS OF EXCLUSION FROM ANALYSIS SETS

The protocol deviations will be reviewed prior to database lock. These will be classified as major or minor.

A deviation will be considered as major if it is likely to significantly bias the interpretation of the primary efficacy endpoint results.

*Note:* In this SAP, major protocol deviations described all deviations leading to exclusion of PP set. There may have protocol deviations identified as major by clinical team (in CTMS) that will not lead to exclusion of PP set. All deviations recorded in CTMS will be reviewed prior to database snapshot/lock to identify any potential deviations leading to exclusion of PP set.

Major protocol deviations and additional reasons of exclusion from analysis sets will be qualified in accordance with the list of pre-defined reasons for exclusion from analysis sets for the study. This list, as large as possible, will be described in a specific document, separately from the statistical analysis plan.

The number and percentage of subjects with at least one major deviation will be tabulated by type of major deviations on the Full Analysis Set.

The number and percentage of subjects with at least one minor deviation will be also tabulated by type of minor deviations on the Full Analysis Set.

The number and percentage of subjects with at least one reason of exclusion from analysis sets will be tabulated by type of reason of exclusion on the Full Analysis Set.

In order to describe the impact of the COVID-19 pandemic on the study, the number and percentages of subjects with at least one deviation related to COVID-19 will be tabulated on the Full Analysis Set, for minor deviations, major deviations and both combined. Type of minor and major deviations will also be described on the Full Analysis Set.

Same description will be performed for the number of deviations reported. Deviations related to COVID-19 pandemic are reported with a prefix “COVID19”. Prefix will not be displayed in the outputs.

## **11. HANDLING OF MISSING DATA AND ANALYSIS OF DROP-OUTS**

### **11.1. DROP-OUTS**

No missing data due to drop out will be imputed.

### **11.2. MISSING DATA (OTHER THAN DROP-OUT)**

#### **11.2.1. Missing efficacy data**

Missing values will not be substituted by estimated values but considered as missing in statistical analysis.

Note: For tumor assessment, when no imaging/measurement is done at all at a particular time point, the patient is not evaluable (NE) at that time point and will be analysed as such.

#### **11.2.2. Missing Safety data**

For laboratory data, in the case that an upper limit is mentioned in the associated character variable, missing numerical value will be replaced by the limit mentioned in the character variable. (For lower limit, missing numeric value will be replaced by the lower limit).

Example: for a measure of ALAT with a character variable “<4”, missing numeric value will be replaced by 4.

Missing numeric values with an associated character variable “>50” will be replaced by 50. In listings, character variable will be displayed.

In case of missing BSA at an assessment time, the measurement at the previous assessment time will be used for the Cetuximab exposure analysis.

### **11.2.3. Missing QoL data**

#### **EORTC QLO-C30**

For each of the 15 scores:

- if at least half of the items from the score have been answered, the score will be calculated based on the mean of the present items.
- If more than half of the items are missing, the score will be missing.
- None single-item scores can be imputed

#### **EQ-5D-5L and PGIC**

Missing item scores will not be substituted by estimated values but considered as missing for statistical analysis.

### **11.2.4. Missing or incomplete dates**

Replacement of missing or incomplete dates presented hereafter is defined in a conservative approach.

#### **▪ Missing dates of first study treatment administration**

Missing dates of the first study treatment administration will be considered equal to the Cycle1 Day 1 visit date for subjects assigned to treatment and with confirmation that this subject actually received treatment.

#### **▪ Missing dates of start of adverse event**

In case of completely missing date, it will be estimated by the date of first study treatment administration.

If the day and the month are missing,

- If the year is the same as the year of first study treatment administration, it will be estimated by the date of first study treatment administration.
- If the year is prior to the year of first study treatment administration, it will be estimated by the 31 December.
- If the year is after the year of first study treatment administration, it will be estimated by the 1st January.

If only the day is missing,

- If the month/year are the same as the month/year of first study treatment administration, it will be estimated by the date of first study treatment administration.
- If the month/year are prior to the month/year of first study treatment administration, it will be estimated by the 15th day of the month.
- If the month/year are after to the month/year of first study treatment administration, it will be estimated by the first day of the month.

If after imputation, the estimated start date is after the end date of the adverse event, it will be replaced by the end date of the adverse event

▪ **Missing dates of end of adverse event**

For adverse events that are not “ongoing” at the end of the study (i.e. with an outcome other than “Not recovered/not resolved” or “Recovering/resolving”), completely missing AE end dates will be estimated by the last contact date.

For adverse event with a start date and which are “ongoing”, completely missing AE end date will be imputed to the cut-off date.

If the day and the month are missing,

- If the year is the same as the year of last contact date, it will be estimated by the last contact date

- If the year is prior to the year of last contact date, it will be estimated by the 31 December

If only the day is missing,

- If the month/year are the same as the month/year of last contact date, it will be estimated by the last contact date
- If the month/year are prior to the month/year of last contact date, it will be estimated by the last day of the month

If after imputation, the estimated end date is before the start date of the adverse event, it will be replaced by the start date of the adverse event.

- **Missing or incomplete time of onset of adverse event**

In case of completely missing time:

- If the onset date is the same as the date of the first study treatment administration, time will be estimated by the time of the first study treatment administration.

- **Prior and Concomitant medications and Procedures (except antineoplastic)**

Start date:

Missing or incomplete start dates will be imputed using the same rules as for start date of adverse event, except if “taken Prior to the study entry” was ticked “Yes”, where the following rules apply: If the start date is completely missing, it will be estimated by the date of ICF signed - 1 (i.e. the day before)

If the day and the month are missing,

- If the year is the same as the year of ICF signed, it will be estimated by the date of ICF signed - 1
- If the year is prior to the year of ICF signed, it will be estimated by the 31st December

If only the day is missing,

- If the month/year are the same as the month/year of the ICF signed, it will be estimated by the date of ICF signed - 1

- If the month/year are prior to the month/year of the ICF signed, it will be estimated by the 15th day of the month

End date:

Missing or incomplete end dates will be imputed using the same rules as for end date of adverse event.

▪ **Prior and subsequent antineoplastic therapies (Medications/Surgeries/Radiotherapies)**

• ***Prior antineoplastic therapies:***

These rules apply to all prior antineoplastic therapies collected, i.e. medications, surgeries and radiotherapies.

Start date:

Missing or incomplete start dates will be imputed using the following rules:

If the start date is completely missing, it will be estimated by the first study treatment administration - 1 (i.e. the day before)

If the day and the month are missing,

- If the year is the same as the first study treatment administration, it will be estimated by the date of first study treatment administration - 1
- If the year is prior to the year of first study treatment administration, it will be estimated by the 31st December

If only the day is missing,

- If the month/year are the same as the month/year of the first study treatment administration, it will be estimated by the date of first study treatment administration – 1
- If the month/year are prior to the month/year of the first study treatment administration, it will be estimated by the 15th day of the month

End date:

Missing or incomplete end dates will be imputed using the same rules as for end date of adverse event.

- ***Subsequent antineoplastic therapies:***

These rules apply to all subsequent antineoplastic therapies collected, i.e. medications (both start and end dates), surgeries (start date only) and radiotherapies (start and end dates).

Start date:

Missing or incomplete start dates of subsequent antineoplastic therapies will be imputed using the following rules:

If the start date is completely missing, it will be estimated by the EOT decision date + 1 (i.e. the day after)

If the day and the month are missing,

- If the year is the same as the EOT decision date, it will be estimated by the EOT decision date + 1
- If the year is posterior to the year of the EOT decision date, it will be estimated by the 1st January

If only the day is missing,

- If the month/year are the same as the month/year of the EOT decision date, it will be estimated by the EOT decision date + 1
- If the month/year are posterior to the month/year of the EOT decision date, it will be estimated by the first day of the month

NB: "EOT decision date" refers to the date collected on the "End-of-treatment" disposition form of the e-CRF.

End date:

Missing or incomplete end dates will be imputed using the same rules as for end date of adverse event.

As radiotherapies cannot be reported as “ongoing”, completely missing end date of radiotherapy will be imputed to the cut-off date.

▪ **Date of death**

Missing or partial dates of death will be imputed as follows:

- If only the day is missing: 1st day of the month and year of death
- If the day and the month are missing: January 1st of the year of death
- If the date is completely missing: it will be estimated by the last contact date

If after imputation: death date < last contact date, then it will be estimated by the last contact date.

▪ **Date of initial diagnosis of primary site**

Completely missing dates will not be imputed.

Partial dates of initial diagnosis of primary site will be imputed as follows:

- If only the day is missing:
  - If the month/year are the same as the month/year of the first study treatment administration: it will be estimated by the first study treatment administration – 1 (i.e. the day before)
  - If the month/year are before the month/year of the first study treatment administration: it will be estimated by the 15th day of the month
- If the day and the month are missing:
  - If the year is the same as the year of the first study treatment administration: it will be estimated by the first study treatment administration – 1 (i.e. the day before)
  - If the year is before the year of the first study treatment administration: it will be estimated by the 1st of July

▪ **Date of first metastasis**

Missing or partial dates of first metastasis will be imputed as described for date of initial diagnosis of primary site. If after imputation: date of first metastasis < date of initial diagnosis of primary site, then the date of first metastasis will be considered same as the date of initial diagnosis of primary site.

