5.7.2. Study Discontinuation for individual Subject

The subject may be considered discontinued from the study for the following reasons:

- Withdrawal of consent.
- Lost to follow-up.
- Death.
- Termination of the study by the Sponsor.

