10.2.3. Follow-up of SAEs

The Investigator will provide follow-up information regarding a reported SAE using the SAE form providing the results of relevant examinations, laboratory and diagnostic tests, and hospitalisation records as needed.

Investigators must follow subjects with AEs/SAEs until the event has resolved, the condition has stabilized, withdrawal of consent, subject is lost to follow-up or death OR until 30 days after the last dose of study drug, whichever occurs first. Ongoing treatment-related AEs/SAEs may be followed beyond the 30-day follow-up period if clinically indicated.

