13.6. HANDLING OF DROPOUTS AND MISSING DATA

As of the date of data-cutoff for the primary CSR for the purposes of reporting:

Subjects continuing to receive study drugs at the time of analysis will have time-to-event data (e.g., PFS, DOR) censored at the time of last tumor assessment prior to the data cut-off point used. Ongoing events (e.g., AEs, concomitant medication, etc.) will be summarized using the data cut-off date as the date of completion, with an indication that the event is ongoing.

For subjects who drop out from the study with ongoing events, the discontinuation date will be used as the completion date of the event with the appropriate censoring.

The reason for discontinuation from study will be summarized, along with the dates of first and last study drugs, duration of exposure to study drugs and date of discontinuation for each subject.

Specific details regarding the handling of missing data will be included in the statistical analysis plan.

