### **Groupings of adverse events**

Such groups (see Appendix 3) consist of one or more AEs (MedDRA Preferred Terms) and for which there is a specific clinical interest regarding the study treatment.

Grouping of AEs will be summarized as follows:

- Overall summary of each grouping, including the number of subjects with at least one AESI of the grouping, at least one related AESI, at least one serious AESI, at least one AESI leading to study treatment discontinuation, at least one AESI leading to study treatment interruption, at least one AESI leading to dose reduction, at least one AESI requiring corrective treatment/procedure, and the associated numbers of occurrences.
- Number and percentage of subjects with at least one TEAESI by grouping and PT, and by maximum grade (Grade 1 to Grade 5).
- Number and percentage of subjects with at least one TEAESI by grouping and PT, and worst outcome

The onset day of first occurrence of any TEAESI from the grouping will be described by grouping and Preferred Term (PT), overall and maximum Grade 3 or higher.

For each grouping, the maximum duration of TEAESI occurrences for subjects with at least one TEAESI from the considered grouping will be also described by Preferred Term (PT), overall and maximum Grade 3 or higher. For the calculation of the duration, end date of TEAESI will be imputed according to rules described in section 11.2.4 (AE end dates).

All AEs will be included in the listings of individual data.

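### SAP 11.2.4, which SAP 15.2 uses for AESI duration, sets no limit at death, so a subject who died with an unresolved event can be given a duration that runs past death

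*SAP*

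**What the plan says.** SAP 11.2.4 gives two rules for an adverse event with no end date at all. If the outcome is not one of the ongoing ones (Not recovered/not resolved, Recovering/resolving), "completely missing AE end dates will be estimated by the last contact date". If the event has a start date and is ongoing, the "completely missing AE end date will be imputed to the cut-off date". Partial end dates are completed by reference to the last contact date.

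SAP 15.2, under Groupings of adverse events, describes the maximum duration of TEAESI occurrences by preferred term, overall and for maximum grade 3 or higher. It states: "For the calculation of the duration, end date of TEAESI will be imputed according to rules described in section 11.2.4 (AE end dates)". It does not mention SAP 9.5 or censoring.

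SAP 9.5 sends ongoing events to the cut-off in general, with an indication that they are ongoing, but has a separate rule for early leavers: "For subjects who drop out from the study with ongoing events, the discontinuation date will be used as the completion date of the event". Protocol 13.6 says the same: "the discontinuation date will be used as the completion date of the event with the appropriate censoring". Neither section mentions death. Protocol 5.7.2 does, in a list introduced by "The subject may be considered discontinued from the study for the following reasons", alongside withdrawal of consent, loss to follow-up and termination by the Sponsor.

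**The concern.** An adverse event cannot outlast the subject, and Protocol 10.2.3 lists "withdrawal of consent, subject is lost to follow-up or death" among the points at which follow-up of an event stops. A rule that runs an unresolved event to the cut-off in a subject who has died therefore produces an impossible duration. That duration measures how early the subject enrolled and when the data were cut, not how long the toxicity lasted.

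Deaths well before cut-off are to be expected. Protocol 1.1 cites a median survival of about 12 to 14 months in this population, and the Main study period runs from November 2018 to 27 December 2020. SAP 9.2 includes the minimum and maximum among its standard summary statistics, so a single affected subject can set the maximum reported for an AESI grouping.

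**Working it through.** **The rules side by side.** The documents state no AE-duration figure to reproduce, so the first check is one of text.

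| Situation | Imputed end | Source |
|---|---|---|
| Ongoing event, start date known, end date wholly missing | Cut-off | SAP 11.2.4 |
| Event not ongoing (including outcome Fatal or Unknown), end date wholly missing | Last contact | SAP 11.2.4 |
| Partial end date | Resolved against last contact | SAP 11.2.4 |
| Ongoing event, subject drops out | Discontinuation date | SAP 9.5, Protocol 13.6 |
| Ongoing hospitalisation | Last contact | SAP 18 |
| Ongoing event, subject dies | Not named in SAP 9.5 or 11.2.4 | – |

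Two events in the same deceased subject, both without an end date, can therefore end on different dates. One recorded as Unknown stops at last contact; one recorded as Not recovered runs to cut-off. SAP 11.2.4 checks that an event does not end before it starts. It also has a consistency check on the date of death: "If after imputation: death date < last contact date, then it will be estimated by the last contact date". It has no check that an event ends by death.

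**Size, by illustration.** The documents give no event times, so these inputs are assumed: onset on study day 30, event unresolved, death on study day 274, first dose on 1 Dec 2018 or 1 Jul 2019.

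- Duration (SAP 9.1.3) = end − onset + 1.
- Onset to death = 274 − 30 + 1 = 245 days in both cases.
- Death falls on 31 Aug 2019 or 30 Mar 2020.
- Excess = cut-off − date of death.

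**Which cut-off.** Protocol 13.1 plans the CSR at the primary analysis, and SAP Appendix 5 puts all listed analyses except PK and healthcare resource use into Stage 2. The Stage 2 cut-off follows four post-baseline tumour assessments and an opportunity for a confirmation scan. The last enrolled subject started treatment on 27 Dec 2019. Assessments fall at weeks 6, 12, 20 and 28, and 28 × 7 = 196 days leads to 10 Jul 2020. One further 8-week scan (56 days) leads to 4 Sep 2020. This is an estimate. The Main study period ends on 27 Dec 2020.

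| First dose | Cut-off | Imputed duration (days) | Onset to death (days) | Excess (days) |
|---|---|---|---|---|
| 1 Dec 2018 | 10 Jul 2020 | 559 | 245 | 314 |
| 1 Dec 2018 | 4 Sep 2020 | 615 | 245 | 370 |
| 1 Dec 2018 | 27 Dec 2020 | 729 | 245 | 484 |
| 1 Jul 2019 | 10 Jul 2020 | 347 | 245 | 102 |
| 1 Jul 2019 | 4 Sep 2020 | 403 | 245 | 158 |
| 1 Jul 2019 | 27 Dec 2020 | 517 | 245 | 272 |

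The imputed value does not depend on the date of death. With onset on 1 Jun 2019 and cut-off on 27 Dec 2020 it is 576 days, whether death came on 1 Jul 2019 (31 days after onset, counted inclusively) or on 1 Dec 2020 (550 days).

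**Effect on the mean.** If k of n subjects in a grouping are affected, the mean rises by (k/n) × excess. With assumed k = 1 and n = 20, this is 102/20 = 5.1 to 370/20 = 18.5 days at the estimated Stage 2 cut-off, and 272/20 = 13.6 to 484/20 = 24.2 days at 27 Dec 2020. The median may not move.

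**The case against.** The strongest reply is that the SAP already holds the right rule. SAP 11.2.4 sits under a heading that excludes drop-out data, SAP 11.1 says that data missing because of drop-out are not imputed, and SAP 9.5 tells the analyst to close such events at discontinuation with censoring. Since Protocol 5.7.2 counts death as a study discontinuation, 9.5 can be read to cover deaths, and the time after death is then zero.

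Much of this stands. A reader might infer that the SAP sets no limit at study exit, or that 11.2.4 flatly contradicts 9.5 for drop-outs. The documents do not support that: the two sections can be read as a general rule beside a specific one, with a missing link between them. Nor is a post-death duration inevitable; it arises when 15.2 is followed as written.

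The reply does not dispose of the point. SAP 15.2 sends the programmer to 11.2.4 by number and nowhere else. The heading does not keep 11.2.4 clear of deaths, because that section itself imputes dates of death. No part of the SAP says that death counts as dropping out.

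A further reply is that readers can see unresolved events: 9.5 asks for them to be indicated, 15.2 tabulates worst outcome, and listings show dates as reported. That is true, but a flag does not correct the summarised duration. SAP 11.2.4 also describes its rules as conservative. Overstating duration hides no harm, but days after death are still not toxicity.

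**Conclusion.** The point holds as a minor one. For an ongoing AESI with a start date and no end date, in a subject who died before cut-off, the derivation that 15.2 prescribes gives a duration that includes time after death. The excess equals the gap from death to cut-off. In the assumed examples this is roughly 100 to 370 days at the estimated Stage 2 cut-off and 272 or 484 days at the end of the Main study period. These figures rest on assumed onset, death and first-dose dates and an estimated Stage 2 date. The documents do not say how many subjects would be affected.

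A reader might infer that every ongoing event runs to cut-off. That is too broad: a start date, an ongoing outcome and a wholly missing end date are all required, and fatal events and partial dates go by last contact. A reader might also infer a wider effect on the safety results or on efficacy. There is none: AESI incidence, grade and onset and the primary endpoint do not use this end date, and the duration summaries are descriptive. For living subjects off treatment, 9.5 and 11.2.4 agree on the cut-off. Some of that time may be unobserved, but Protocol 10.2.3 allows treatment-related events to be followed beyond 30 days, so no criticism is made there.

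**What to change.** - In SAP 11.2.4, end an ongoing event with no end date at the earliest of cut-off, death and study discontinuation.
- Cross-refer SAP 9.5 from both 11.2.4 and 15.2, and name death in 9.5, so that one rule governs.
- In 15.2, flag these durations as censored, as 9.5 already requires for drop-outs. A separate table for unresolved durations is optional.

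The cost is one sentence, two cross-references, one added word in 9.5 and a small derivation change. It uses death and discontinuation dates that the SAP already relies on, and needs no new data.

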9.1.10.2. Survival Visit (every 3 months) _ Main study period

The Survival follow-up period will start after the completed 30 days safety follow up, until the End of Study.

If a subject discontinues the treatment for a reason other than progressive disease, tumor assessment must be performed (as per local and central review) until the start of a new anti-cancer therapy, disease progression, death, lost to follow-up, subject decision or withdrawal of consent. Subjects who discontinue the treatment will be contacted by phone every 3 months (or more frequently as needed) for collection of information during the survival follow-up period:

- Survival status
- Documentation of subsequent anticancer therapy
- Documentation of the date of progressive disease following the initiation of subsequent anticancer therapies

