**Table 12: Censoring rules for PFS**

In the below table, “new antineoplastic therapy” refers to any additional secondary antineoplastic medication or anti-cancer surgery or radiotherapy.

	Situation	Event Date	Outcome
No baseline tumor assessments			
A1	No baseline assessment and death after the second scheduled post-baseline tumor assessment, or no death	Date of first study treatment administration	Censored
A2	No baseline assessment and death on or before the second scheduled post-baseline tumor assessment	Date of death	Event
No post-baseline tumor assessments (without new antineoplastic therapy given)			
B1	Death on or before the second scheduled post-baseline tumor assessment	Date of death	Event
B2	Death after the second scheduled post-baseline tumor assessment or no death	Date of first study treatment administration	Censored
With baseline and post-baseline tumor assessments (without new antineoplastic therapy given prior progression or death without progression observed)			
C1	Progression with zero or one missed/inadequate tumor assessment prior to progression	Date of progression	Event
C2	Death but no progression, with zero or one missed/inadequate tumor assessment prior to death	Date of death	Event
D1	Progression but two or more consecutively missed/inadequate tumor assessments prior to progression	Date of last adequate tumor assessment*	Censored
D2	Death without progression, but two or more consecutively missed/inadequate tumor assessments prior to death	Date of last adequate tumor assessment*	Censored
E	No progression, no death	Date of last adequate tumor assessment*	Censored
F	Treatment discontinuation due to ‘Disease progression’ without documented progression, i.e. clinical progression based on investigator claim	N/A (not considered as an event, patient without documented PD should be followed for progression after discontinuation of treatment)	Information ignored
Initiation of new antineoplastic therapy given prior progression or death without progression observed			
G	New antineoplastic therapy started before progression or death	Date of last adequate tumor assessment prior to initiation of new antineoplastic therapy*	Censored
H	No post-baseline tumor assessment and new antineoplastic therapy started prior to a death	Date of first study treatment administration	Censored

\* tumor assessment with non-missing and non-unknown overall lesion response, as defined in section 9.3.

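### Partial start dates of subsequent therapy are imputed without a check against documented progression, so a PD dated after the end-of-treatment decision can become a censored PFS or DOR time

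*SAP*

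**What the plan says.** SAP 11.2.4 opens with a general claim: "Replacement of missing or incomplete dates presented hereafter is defined in a conservative approach". Its rules for the start of subsequent antineoplastic therapy (medication, surgery or radiotherapy) are anchored on the EOT decision date:

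- Completely missing: "If the start date is completely missing, it will be estimated by the EOT decision date + 1".
- Year only, same year as the EOT decision: "If the year is the same as the EOT decision date, it will be estimated by the EOT decision date + 1".
- Year only, later year: 1 January of that year.
- Month and year, same month as the EOT decision: EOT decision date + 1.
- Month and year, later month: "If the month/year are posterior to the month/year of the EOT decision date, it will be estimated by the first day of the month".

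None of these branches refers to tumor assessments or to documented progression.

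The imputed date then feeds the censoring tables. In Table 12 row G, a subject whose new therapy started before progression or death is censored at the "Date of last adequate tumor assessment prior to initiation of new antineoplastic therapy". Table 13 (PFS sensitivity) repeats row G, and Table 14 row F does the same for DOR. SAP 14.2.5 and 14.2.8 handle central-review PFS and DOR in a similar way. Protocol 13.8.2 contains the parent censoring rule but says nothing about imputed dates.

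Protocol 8.1 and SAP 6.1 require scans to continue when treatment stops for a reason other than progression, so PD after the EOT decision is foreseen.

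**The concern.** Row G is meant for subjects who really did start new therapy before progressing. When the start date is partial, the order of PD and therapy is unknown, and the SAP settles it by always choosing the earliest date its rules allow. For a subject with PD after the EOT decision, that can reverse the true order. The documented event disappears and is replaced by censoring at the scan before the imputed start. Losing events and censoring earlier both push the PFS and DOR curves upward, which is the opposite of conservative.

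No planned analysis would show this. The only PFS sensitivity analysis changes the rule for two or more missed assessments and leaves row G alone. Elsewhere 11.2.4 does check imputed dates for consistency: AE start against AE end, death against last contact, first metastasis against diagnosis. The corresponding check against documented PD is absent.

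**Working it through.** The plan attaches no figure to this rule, so there is none to reproduce. The check has three parts.

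**1. The rule as an algorithm.** Let E be the EOT decision date and S* the imputed start. Then S* = E + 1 if the date is wholly missing or the recorded month (or year, if only that is known) is the same as E's. Otherwise S* is the 1st of the recorded month or 1 January of the recorded year. Row G or row F applies if S* falls before the PD date. S* is never earlier than E + 1, so any PD dated on or before E stays an event.

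**2. Dated examples.** First, one subject in detail: EOT decision 10 Feb 2020 for toxicity, last scan SD on 22 Jan, next scheduled scan PD on 18 Mar, second line actually begun 27 Mar but recorded only as March 2020. S* = 1 Mar, which precedes 18 Mar, so row G censors on 22 Jan. With the true date, row C1 gives an event on 18 Mar. The gap is 9 + 29 + 18 = 56 days: one 8-week scan interval, with no missed scan.

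Seven further hypothetical subjects cover the branches:

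| # | EOT decision (reason) | PD | Start as recorded | S* | PFS by SAP | PFS with latest compatible date |
|---|---|---|---|---|---|---|
| 1 | 15 Feb 2020 (AE) | 12 Mar 2020 | Mar 2020 | 1 Mar | censored | event |
| 2 | 12 Mar 2020 (PD) | 10 Mar 2020 | Mar 2020 | 13 Mar | event | event |
| 3 | 5 Mar 2020 (AE) | 20 Mar 2020 | Mar 2020 | 6 Mar | censored | event |
| 4 | 10 Feb 2020 (AE) | 20 Jun 2020 | 2020 | 11 Feb | censored | event |
| 5 | 12 Mar 2020 (PD) | 10 Mar 2020 | 2020 | 13 Mar | event | event |
| 6 | 12 Mar 2020 (PD) | 10 Mar 2020 | Apr 2020 | 1 Apr | event | event |
| 7 | 10 Dec 2019 (AE) | 20 Jun 2020 | 2020 | 1 Jan 2020 | censored | event |

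Four of seven flip, and in all four the PD follows the EOT decision. The three whose PD led to the decision keep their event. These cases show the mechanism; they are not an estimate of frequency.

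**3. Possible size.** Assumptions: exponential PFS; scans at day 42, day 84, then every 56 days; administrative censoring at about 12–23 months; and a share q of observed PDs moved to censoring at the previous scan. The mean Kaplan-Meier median (months) changes as follows:

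| n, underlying median | q = 2% | q = 5% |
|---|---|---|
| 95, 5.5 | 6.47 to 6.58 (+0.11) | 6.47 to 6.70 (+0.23) |
| 90, 5 | +0.13 | +0.32 |
| 90, 8 | +0.25 | +0.51 |

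Neither q nor the underlying medians are given in the documents as values for this trial.

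**The case against.** The strongest objection is about reach. A reader might infer that any progression in the same month or year as a partial therapy date is lost. The documents do not support that. Protocol 5.7.1 makes PD a reason to stop treatment, so the PD that ends treatment is ordinarily dated on or before the EOT decision and is protected. What remains needs two things together: PD after the decision, and an incomplete therapy date. This stands, and it limits the point.

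A second tempting inference is that partial dates will be common because "Subjects who discontinue the treatment will be contacted by phone every 3 months". The documents say nothing about how complete the dates are. The affected subjects are mainly those still attending scans, and Protocol 12.4 requires queries to be resolved before lock. Nor do the documents show that therapy usually follows PD in this subgroup. Someone who stopped for toxicity may start a new line first, and then row G works as intended.

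Third, the endpoints are secondary, and SAP 8 treats everything except the primary test as exploratory. It would be wrong to infer that the primary result is inflated. SAP 14.1 counts only scans before further therapy, so an early imputed start can only remove scans and lower cORR. It also shortens time to subsequent therapy (Table 17).

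Fourth, the size is small against sampling noise. In the n = 95 simulation the standard deviation of the median between replicates is about 0.95 months. With scans exactly on the grid, the typical (median) estimate stays at 6.44 months for q of 0%, 2% and 5%.

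The summary of censor status promised in SAP 14.2.4 gives some visibility, but it does not call for separating imputed from recorded therapy dates. None of these objections removes the defect: followed exactly, the rule can discard a documented PD in the favourable direction.

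**Conclusion.** The concern holds in a limited form. For subjects with RECIST PD dated after the EOT decision and an incomplete start date for subsequent therapy, SAP 11.2.4 combined with row G or row F can turn a documented event into earlier censoring. For PFS and DOR the rule is therefore not conservative, contrary to the SAP's own description, and Table 13 cannot reveal it. The description does hold for cORR and time to subsequent therapy, and the primary test is unaffected.

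If 2–5% of PDs were reversed, mean simulated median PFS would rise by about 0.1–0.5 months for underlying medians of 5 to 8 months. That range rests on an assumed share and an exponential model; it is not an estimate for this trial. The mechanism itself follows directly from the text. It deserves a correction because the change is small and specific.

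**What to change.** Add one sentence to SAP 11.2.4, limited to PFS and DOR. If a subject has RECIST PD documented on a study tumor assessment, and the recorded part of the therapy start date is compatible with a start after that PD, impute PD date + 1; otherwise keep the current rule. In the detailed example this gives 19 Mar, and the PD of 18 Mar stays an event. Requiring a study tumor assessment keeps out progression on the next line, which the protocol collects separately during survival follow-up.

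At minimum, leave the main rule and add a PFS and DOR sensitivity analysis that uses the latest compatible start date, capped at the data cut-off. Under either option, report how many therapy start dates were partial or missing.

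Leave BOCR/BOR and time to subsequent therapy as they are. A later imputed start for BOCR could admit scans taken after new therapy and could only raise the primary cORR.

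The cost is one sentence and little programming. Median PFS and DOR may become slightly less favourable, and a PD that truly followed new therapy may occasionally be counted as an event.
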